## 19.1. DERIVATION

LLOQ is 0.0500 ng/mL for R-amisulpride and S-amisulpride and LLOQ is 1.56 ng/mL for plasma prolactin.

Below derivations apply after concentrations lower than LLOQ are set to  $\frac{1}{2}$  LLOQ.

- Coefficient of variation  
$$100 * \text{Standard Deviation} / \text{Mean}$$
- Geometric Mean  
$$\text{Exponential}(\text{mean of } \log_e \text{ transformed data})$$
- Geometric CV  
$$\text{Square Root}(\text{Exponential}(\text{Variance}(\log_e \text{ transformed data}) - 1)) * 100$$

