## 19. PHARMACOKINETIC ANALYSIS

All PK analysis will be performed using Safety population.

Blood sample for plasma concentrations of R-amisulpride, S-amisulpride, total amisulpride, and/or plasma prolactin measurement will be collected at: Visit 1E (coinciding with Visit 9 of SEP380-301), Visit 2E, Visit 4E, Visit 6E, Visit 8E, Visit 10E, Visit 12E, Visit 14E, and Visit 15E/Follow-up. Any plasma concentration or summary statistics below the lower limit of quantification (LLOQ) will be represented by "BLQ" (below the limit of quantification) in tables and listings. Amisulpride plasma concentration will not

be presented for the placebo group.

R-amisulpride, S-amisulpride, total amisulpride, and plasma prolactin concentrations at each scheduled sample collection time point (including ET and Follow-up, see [Section 7.4](#) for mapping of the ET visit) will be summarized descriptively (n, mean, median, minimum, maximum, coefficient of variation [CV] and if appropriate, geometric mean and geometric CV [GCV]). In addition, if there is at least 1 concentration < LLOQ within a treatment group at a time point, it will be set to  $\frac{1}{2}$  LLOQ for summary statistics calculations. Number and percentage of concentrations that are below the LLOQ will be provided for each visit. All PK summaries will be presented.

Population PK analysis methods will be used to characterize the PK/PD profiles in subjects treated with SEP-4199 CR. Analysis methods and results of population PK and PD analysis will be described in a separate document from the SAP and clinical study report.

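### The geometric CV formula in SAP 19.1 subtracts 1 inside the exponential, so it can never return less than 60.7% and is right at only one value

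*SAP*

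**What the plan says.** SAP Section 19 summarises "R-amisulpride, S-amisulpride, total amisulpride, and plasma prolactin concentrations at each scheduled sample collection time point" descriptively. The listed statistics include the arithmetic CV and, "if appropriate, geometric mean and geometric CV [GCV"]. Section 19.1 then defines three derived statistics:

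- Arithmetic CV: 100 times the standard deviation over the mean.
- Geometric mean: "Exponential}(\text{mean of } \log_e \text{ transformed data"), so the scale is the natural log.
- Geometric CV: "Square Root}(\text{Exponential}(\text{Variance}(\log_e \text{ transformed data}) - 1)) * 100".

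The same section says "Below derivations apply after concentrations lower than LLOQ are set to" half that limit. Neither document gives another geometric CV formula that would override this one. SAP Section 5.3 has the final analyses carried out according to the SAP, and this version is marked final.

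**The concern.** The closing bracket of the exponential comes after the subtraction instead of before it. The 1 is therefore subtracted from the variance of the logs, not from the exponentiated variance. This is a different function of the data, not a rounding or notational variant.

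Plasma concentrations of the two enantiomers and of prolactin are the study's PK/PD endpoints (protocol Section 6.3, SAP Section 3.2.4), and the geometric CV is the log-scale measure of spread offered for them. If programmed as written:

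- No group or visit could show a geometric CV below 60.7%, however consistent the concentrations were.
- Differences in spread would be compressed, most strongly where variability is low.
- Markedly variable data would look less variable than they are.
- A single table could carry an arithmetic CV and a geometric CV that cannot be reconciled.

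**Working it through.** **Inputs.** The printed formula and its neighbours come from SAP 19.1, and the analytes from SAP 19. The documents give no log-scale variance and no expected geometric CV, so the true values below are assumed, from 0% to 300%. There is no figure in the plan to reproduce.

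**Step 1: read the brackets.** The opening and closing brackets balance. At the point of subtraction two are still open, those of the square root and the exponential. With v = variance of the natural-log concentrations:

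- Printed: P(v) = 100 × sqrt(exp(v − 1)) = 100 × exp((v − 1)/2)

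**Step 2: the correct expression.** If ln X is normal with mean m and variance v, then X has mean exp(m + v/2) and variance exp(2m + v) × (exp(v) − 1). Standard deviation over mean gives:

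- Correct: G(v) = 100 × sqrt(exp(v) − 1)

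**Step 3: zero-spread check.** Let every concentration be equal, so v = 0.

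- Arithmetic CV in the same section: SD = 0, so 0%.
- Correct geometric CV: 100 × sqrt(1 − 1) = 0%.
- Printed geometric CV: 100 × exp(−0.5) = 60.653%, or 60.7%.

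P increases with v and v cannot be negative, so 60.7% is the floor. The case can occur under the plan's own rules: if all values in a group at a visit were below the quantification limit and set to half of it, v would be exactly 0.

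**Step 4: size across a range.** For a true geometric CV of g (as a proportion), v = ln(1 + g²), so P = 100 × sqrt((1 + g²)/e).

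| True geometric CV (assumed) | v | Printed formula | Printed ÷ true |
|---|---|---|---|
| 10% | 0.0100 | 60.96% | 6.096 |
| 20% | 0.0392 | 61.85% | 3.093 |
| 30% | 0.0862 | 63.32% | 2.111 |
| 50% | 0.2231 | 67.81% | 1.356 |
| 80% | 0.4947 | 77.67% | 0.971 |
| 100% | 0.6931 | 85.78% | 0.858 |
| 150% | 1.1787 | 109.34% | 0.729 |
| 200% | 1.6094 | 135.62% | 0.678 |
| 300% | 2.3026 | 191.80% | 0.639 |

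True values from 0% to 50% are squeezed into 60.7% to 67.8%.

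**Step 5: where the two agree.** Setting exp(v − 1) = exp(v) − 1 gives exp(v) × (1 − 1/e) = 1, so v = −ln(1 − 1/e) = 0.4587. There both formulas give 76.29%. Below that point the printed rule overstates. Above it the rule understates, and the ratio falls towards exp(−0.5) = 0.607.

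**The case against.** Nobody can defend the formula as printed, so the case on the other side concerns certainty and weight.

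- **The text was machine-read from a PDF.** The point turns on one closing bracket, so the original page is worth a look. However, the brackets balance and the two neighbouring formulas read correctly, so nothing indicates a reading fault.
- **A competent programmer will use the right formula.** Possibly. The outputs would then differ from the derivation in the final SAP, and the text would still need correcting.
- **The printed rule still ranks groups correctly.** This stands. The function rises strictly with variance, so contrasts are compressed rather than erased, and near 76% the error is small: 70% would print as 74.0% and 80% as 77.7%.
- **Little depends on it.** This also stands. The statistic is descriptive and optional, and the same table carries the mean, median, range and a correctly defined arithmetic CV. Population PK/PD methods and results are documented separately. The serum prolactin summaries in SAP 18.2 specify no geometric CV. The study makes no inference (SAP 7.6), and 64 subjects were enrolled (SAP 4.4).
- **The actual error in this trial is unknown.** True: it depends on log-scale variances that the documents do not give.

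These points limit the importance. They do not make the formula right.

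**Conclusion.** The formula in SAP 19.1 is wrong as written. Followed literally, it has a floor of 60.7% and misstates every geometric CV except one that happens to equal 76.3%. It inflates low variability (30% becomes 63%) and shrinks high variability (150% becomes 109%).

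The floor and the crossing point follow from the algebra alone. The individual magnitudes assume the true values shown. That any reported value will be wrong assumes that the tables are programmed as printed and that the statistic is reported. The effect is limited to the log-scale spread of R-, S- and total amisulpride and plasma prolactin. No primary safety or effectiveness summary is touched. It should be corrected because the PK tables would otherwise carry wrong numbers, but it does not threaten the study's main conclusions.

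**What to change.** In SAP 19.1, replace the definition with:

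Geometric CV (%) = 100 × Square Root(Exponential(Variance(natural-log transformed data)) − 1)

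Check the bracket against the original page, then confirm that the PK and prolactin table programs use the corrected form. A test on a constant series should return 0%.

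The text change is one bracket. Because the SAP is already final, it also needs a short amendment or documented correction, and a rerun of any PK tables already programmed from the printed rule; the documents do not say whether such tables exist. No new data, assumption or clinical decision is involved.

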## 20. DATA NOT SUMMARIZED OR PRESENTED

The variables and/or domains not summarized or presented are:

- Subject initials.

## APPENDIX 1. PROGRAMMING CONVENTIONS FOR OUTPUTS

### OUTPUT CONVENTIONS

Where applicable, the Appendix\_compilation\_working\_update\_2022Final.pdf document – provided by SMPA – will be followed.

In addition, the following output conventions are to be followed:

- General presentation:
  - The left-hand column should start in column 1. No centering of the output should occur.
  - Rounding should be done with the SAS function ROUND.
  - Numbers in tables should be rounded, not truncated.
  - Alphanumeric output should be left aligned.
  - Numbers should be decimal point aligned.
  - Whole numbers should be right aligned.
  - Text values should be left aligned.
  - The first letter of a text entry should be capitalized.
- Univariate Statistics: If the raw data has N decimal places, then the summary statistics should have the following decimal places:
  - Minimum and maximum: N
  - Mean, median, Q1, and Q3: N + 1
  - SD: N + 2
- Frequencies and percentages (n and %):
  - Percent values should be reported inside parentheses, with one space between the count (n) and the left parenthesis of the percentage. Parentheses should be justified to accept a maximum of 100.0 as a value and padded with blank space if the percent is less than 100.0.
  - Percentages will be reported to one decimal place, except cases where percent < 100.0% but > 99.9% will be presented as '> 99.9%' (e.g., 99.99% is presented as > 99.9%); and cases where percent < 0.1% will be presented as '< 0.1%' (e.g., 0.08% is presented as < 0.1%). Rounding will be applied after the < 0.1% and >99.9% rule.
  - Where counts are zero, no percentage should appear in the output.
- Confidence Intervals:
  - Confidence intervals and estimates are presented to one place more than the raw data, and standard errors to two places more than the raw data.
  - Confidence intervals should be justified so that parentheses displayed on consecutive lines of a table “line up”.
  - Boundary values of confidence intervals should be separated by a comma.
  - Boundary values should be padded as necessary to accept negative values and to allow alignment of the decimal place.
- Ratios should be reported to one more decimal place than the raw data.
- Spacing must be a minimum of 1 blank space between columns (preferably 2).
- Missing values:
  - A “0” should be used to indicate a zero frequency.

- o A blank will be used to indicate missing data in an end-of-text table or subject listing.
- Figures:
  - o Figures should be provided in RTF files using the SAS Output Delivery System (ODS), as Computer Graphics Metafile (CGM) formatted graphical output generated by SAS.
  - o The image should be clear and of high quality when viewed in the Word document, and when printed.
  - o In general, boxes around the figures should be used.
- Footers should be defined as follows:
  - o A continuous line of underscores ('\_') will follow the body of the table or listing prior to any footnotes at the bottom of the page.
  - o Table footnotes should appear directly after the body of the table.
  - o If text wraps across more than one line (for a note), the first letter for all lines of text after the first one will be indented to align beneath the first letter of the text in the first line.

## DATES & TIMES

Depending on data available, dates and times will take the form yyyy-mm-ddThh:mm:ss.

## SPELLING FORMAT

English US.

## PRESENTATION OF TREATMENT GROUPS

For outputs, treatment sequences will be represented as follows and in that order:

Treatment Sequence	For Tables (Column Order)	For Graphs (Order)
Placebo - SEP-4199 CR	PBO-SEP (1)	PBO-SEP (2)
SEP-4199 CR 200 mg/day - SEP-4199 CR	SEP-SEP (2)	SEP-SEP (3)
SEP-4199 CR 400 mg/day - SEP-4199 CR	SEP-SEP (2)	SEP-SEP (3)
	ALL-EXT (3)	ALL EXT (1)

## LISTINGS

All listings will be ordered by the following (unless otherwise indicated in the template):

- Subject ID.
- Visit (where applicable)
- Original date/time (where applicable).

## APPENDIX 2. PARTIAL DATE CONVENTIONS

The actual dates as collected on the CRF will be presented in the listings. Imputed dates will NOT be presented in the listings unless otherwise specified.

### ALGORITHM FOR ADVERSE EVENTS

The algorithm below applies to all SEP380-301/303 AEs and SEP380-301 pre-treatment event records collected in the SEP380-303 clinical database.

Step 1) For events that exist in the SEP380-301 databases and have a missing or partial start date, retrieve imputed event start dates from the respective ADaM dataset.

Events in the SEP380-303 database which also exist in the SEP380-301 databases will be identified based on a comparison of subject ID, PT, AE start date (and time if available), severity, and seriousness.

Step 2) For events that do not exist in the SEP380-301 databases yet the known part of the event start and/or end dates show that the event unambiguously started before first OLE dose in SEP380-303, impute missing or partial event start and/or end dates (if not ongoing) using the algorithm below.

If an event has some missing components in both the start and end dates, first impute the end date.

#### AE end date imputation

- If year and month (YYYY-MM) of AE end date are known, then impute the missing day to be the earlier of (last day of the month; date of SEP380-301 last contact).
- If only year (YYYY) of AE end date is known, then impute the missing month and day to be the earlier of (31st December; date of SEP380-301 last contact).
- If AE end date is completely missing and AE is not ongoing, then impute AE end date to be date of SEP380-301 last contact.

#### AE start date imputation

- If year and month (YYYY-MM) of AE start date are known and YYYY-MM = year and month of SEP380-301 study med start date, then impute AE start date to be the earlier of (SEP380-301 study med start date; full or imputed AE end date [if non-missing]).
- If year and month (YYYY-MM) of AE start date are known and YYYY-MM ≠ year and month of SEP380-301 study med start date, then impute AE start date to be YYYY-MM-01.
- If only year (YYYY) of AE start date is known and YYYY = year of SEP380-301 study med start date, then impute AE start date to be the earlier of (SEP380-301 study med start date; full or imputed AE end date [if non-missing]).
- If only year (YYYY) of AE start date is known and YYYY ≠ year of SEP380-301 study med start date, then impute AE start date to be YYYY-01-01.
- If AE start date is completely missing, then impute AE start date to be the earlier of (SEP380-301 study med start date; full or imputed AE end date [if non-missing]).

Step 3) For the remaining events in SEP380-303 database, impute missing or partial event start and/or end dates (if not ongoing) using the algorithm below.

If an event has some missing components in both the start and end dates, first impute the end date.

#### **AE end date imputation**

- If year and month (YYYY-MM) of AE end date are known, then impute the missing day to be the earlier of (last day of the month; date of SEP380-303 last contact).
- If only year (YYYY) of AE end date is known, then impute the missing month and day to be the earlier of (31st December; date of SEP380-303 last contact).
- If AE end date is completely missing and AE is not ongoing, then impute AE end date to be date of SEP380-303 last contact.

#### **AE start date imputation**

- If year and month (YYYY-MM) of AE start date are known and YYYY-MM = year and month of OLE study med start date, then impute AE start date to be the earlier of (OLE study med start date; full or imputed AE end date [if non-missing]).
- If year and month (YYYY-MM) of AE start date are known and YYYY-MM ≠ year and month of OLE study med start date, then impute AE start date to be YYYY-MM-01.
- If only year (YYYY) of AE start date is known and YYYY = year of OLE study med start date, then impute AE start date to be the earlier of (OLE study med start date; full or imputed AE end date [if non-missing]).
- If only year (YYYY) of AE start date is known and YYYY ≠ year of OLE study med start date, then impute AE start date to be YYYY-01-01.
- If AE start date is completely missing, then impute AE start date to be the earlier of (OLE study med start date; full or imputed AE end date [if non-missing]).

Step 4) Using the full or imputed event dates, assign events into SEP380-301 pre-treatment event, SEP380-301 AE, or SEP380-303 AE as described below.

If both event start date/time and SEP380-303 OLE study med start date/time are available:

- If event start date/time < SEP380-303 OLE study med start date/time, then SEP380-301 pre-treatment event or SEP380-301 AE\*.
- If event start date/time ≥ SEP380-303 OLE study med start date/time, then SEP380-303 AE.

If (event start date is available and time is not available) and/or (SEP380-303 OLE study med start date is available and time is not available):

- If event start date < SEP380-303 OLE study med start date, then SEP380-301 pre-treatment event or SEP380-301 AE\*.
- If event start date > SEP380-303 OLE study med start date, then SEP380-303 AE.
- If event start date = SEP380-303 OLE study med start date and the event record exists in SEP380-301 database§, then SEP380-301 pre-treatment event or SEP380-301 AE\*.
- If event start date = SEP380-303 OLE study med start date and the event record does not exist in SEP380-301 database§, then SEP380-303 AE.

\*The distinction between SEP380-301 pre-treatment event and SEP380-301 AE should be performed as specified in the SEP380-301 SAP.

§Based on a comparison of subject ID, PT, AE start date (and time if available), severity, and seriousness.

## ALGORITHM FOR PRIOR / CONCOMITANT / POST-TREATMENT MEDICATIONS

In case of partial or missing medication start and/or stop dates, impute the partial or missing dates using the algorithm below.

If a medication has some missing components in both the start and stop dates, first impute the stop date.

### Impute stop date as latest possible date

- If only day unknown, impute to the earlier of (last day of the month; date of SEP380-303 last contact).
- If month and day unknown, impute to the earlier of (31st December; date of SEP380-303 last contact).
- If stop date is completely unknown and medication is not ongoing, impute to date of SEP380-303 last contact.

### Impute start date as earliest possible date

CRF questions: 'Started prior to first dose?' = Yes; 'Started after last dose of study medication?' = No.

- If only day unknown, impute to the first day of the month.
- If month and day unknown, impute to the 1st January.
- If start date is completely unknown, impute to the earlier of (date of informed consent\*; full or imputed medication stop date [if not missing]).

CRF questions: 'Started prior to first dose?' = No; 'Started after last dose of study medication?' = Yes.

- If only day unknown, impute to the later of (first day of the month; SEP380-303 OLE study med end date + 1).
- If month and day unknown, impute to the later of (1st January; SEP380-303 OLE study med end date + 1).
- If start date is completely unknown, impute to SEP380-303 OLE study med end date + 1.

CRF questions: 'Started prior to first dose?' = No; 'Started after last dose of study medication?' = No.

- If only day unknown, impute to the later of (first day of the month; SEP380-303 OLE study med start date).
- If month and day unknown, impute to the later of (1st January; SEP380-303 OLE study med start date).
- If start date is completely unknown, impute to SEP380-303 OLE study med start date.

### Then assign a medication into prior, concomitant, or post-treatment

The concept of "date" below should also include time information whenever time is available for both comparators.

- If medication stop date < SEP380-303 OLE study med start date, assign as prior.
- If (SEP380-303 OLE study med start date ≤ medication stop date ≤ SEP380-303 OLE study med end date ) and
  1. medication start date < SEP380-303 OLE study med start date, assign as prior and concomitant.

2. SEP380-303 OLE study med start date ≤ medication start date ≤ SEP380-303 OLE study med end date, assign as concomitant.
- If (medication start date > SEP380-303 OLE study med end date on ongoing) and
  1. medication start date < SEP380-303 OLE study med start date, assign as prior, concomitant, and post-treatment.
  2. SEP380-303 OLE study med start date ≤ medication start date ≤ SEP380-303 OLE study med end date, assign as concomitant and post-treatment.
  3. medication start date > SEP380-303 OLE study med end date, assign as post-treatment.

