## 14. PRIOR AND CONCOMITANT MEDICATIONS

Unless otherwise specified, the concomitant medications summary tables will include the following columns: PBO-SEP, SEP-SEP, and ALL EXT (all rollovers from SEP380-301).

Medications will be coded to Anatomical Therapeutic Chemical (ATC) Levels and Preferred Names according to World Health Organization Drug (WHODRUG) dictionary, Version SEP2021.

Whenever available, the time information should be accounted for in the derivation of prior, concomitant, and post-treatment medications. See [APPENDIX 2](#) for the handling of partial dates for medications.

- Prior medications are medications which started prior to the first dose of OLE study medication.
- Concomitant medications are medications which started at the same time of or after the first dose of OLE study medication and at the same time of or before the last dose of OLE study medication; or started prior to and ended at the same time of or after the first dose of OLE study medication; or started at the same time of or prior to the last dose of OLE study medication and marked as ongoing.
- Post-treatment medications are medications which stopped after the last dose of OLE study medication or ongoing.

Concomitant medication use will be summarized by ATC Level 3 and Preferred Name for the Safety Population by the actual treatment. If ATC Level 3 is missing, then ATC Level 2 will be used. Medications will be sorted by ATC Level 3 alphabetically and by Preferred Name in decreasing frequency in the "ALL EXT" column.

Prior, concomitant, and post-treatment medications will be provided in data listings.

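### SAP Appendix 2 tests a medication's start date where the stop date is needed, so, applied literally, it leaves drugs stopped after the last dose with no category and conflicts with SAP Section 14

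*SAP*

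**What the plan says.** SAP Section 14 gives the definitions. A drug is concomitant if it started between the first and last open-label doses, if it "started prior to and ended at the same time of or after the first dose of OLE study medication", or if it started by the last dose and is marked ongoing. None of these sets an upper limit on the stop date. For the post-treatment class it says: "Post-treatment medications are medications which stopped after the last dose of OLE study medication or ongoing". It refers to Appendix 2 "for the handling of partial dates for medications". Concomitant use is tabulated by ATC Level 3 and preferred name for the Safety Population. Prior and post-treatment drugs are only listed.

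The medication algorithm in SAP Appendix 2 first imputes incomplete dates and then assigns categories. On stop dates it says: "If stop date is completely unknown and medication is not ongoing, impute to date of SEP380-303 last contact". The assignment step has three branches:

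- Branch 1: "If medication stop date < SEP380-303 OLE study med start date, assign as prior".
- Branch 2 opens: "If (SEP380-303 OLE study med start date ≤ medication stop date ≤ SEP380-303 OLE study med end date ) and".
- Branch 3 opens: "If (medication start date > SEP380-303 OLE study med end date on ongoing) and".

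Branch 3 has three sub-rules. The first is "medication start date < SEP380-303 OLE study med start date, assign as prior, concomitant, and post-treatment". The second takes a start between the first and last doses and assigns concomitant and post-treatment. The third takes a start after the last dose and assigns post-treatment.

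**The concern.** Branches 1 and 2 cover stop dates before the first dose and between the first and last doses. The natural third branch is a stop date after the last dose, or ongoing. By testing the start date instead, branch 3 contradicts its own first two sub-rules and leaves a gap.

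The gap can contain real records. Protocol Section 10.3 has medications recorded up to the follow-up visit, 7 ± 2 days after the last dose, so stop dates after the last dose are expected in the data. The imputation rule adds more: an unknown stop date on a non-ongoing drug becomes the last-contact date, which falls after the last dose for anyone who attends follow-up. A stop date with only the day missing goes to the earlier of month-end and last contact, which can also fall after the last dose.

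At stake is the completeness of the only planned table of medication use. That table shows how often the permitted treatments for movement symptoms, akathisia, anxiety and insomnia (protocol Section 10.3.3) were used, which is context for the movement-scale and mood results. An omission of this kind would be silent. SAP Section 4.4 reports 64 subjects enrolled. If all 64 were dosed, one subject is 1/64 = 1.6% of the all-subjects column.

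**Working it through.** The plan states no figure here, so the check is one of logic.

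**Step 1, branch 3 for a drug that is not ongoing.** Let F be the first open-label dose and L the last, with F ≤ L.

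- Condition and sub-rule 1: start > L and start < F. Impossible.
- Condition and sub-rule 2: start > L and F ≤ start ≤ L. Impossible.
- Condition and sub-rule 3: start > L. Possible.

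Sub-rules 1 and 2 can therefore apply only to ongoing drugs, and only if *on* is read as *or*.

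**Step 2, typical cases.** Study days are assumed for illustration: F = 1, L = 360, last contact = 360 + 7 = 367. Appendix 2 is read with *or ongoing*, the reading more favourable to the plan.

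| Start | Stop | Appendix 2 as printed | Section 14 |
|---|---|---|---|
| −20 | −5 | prior | prior |
| −20 | 100 | prior, concomitant | prior, concomitant |
| −20 | 364 | none | prior, concomitant, post |
| −20 | ongoing | prior, concomitant, post | prior, concomitant, post |
| 50 | 100 | concomitant | concomitant |
| 50 | 364 | none | concomitant, post |
| 50 | ongoing | concomitant, post | concomitant, post |
| 50 | unknown, not ongoing, imputed to 367 | none | concomitant, post |
| 362 | 365 | post | post |
| 362 | ongoing | post | post |

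**Step 3, a grid, to see whether any other pattern fails.** Starts were taken every third day from Day −30 to Day 366 (133 values). Stops were taken on each grid day from the start day to Day 366, or ongoing.

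- Combinations: 133 × 134 / 2 + 133 = 8,911 + 133 = 9,044.
- No category as printed: 131 starts on or before Day 360 × 2 stops after it (Days 363 and 366) = 262. All 262 are non-ongoing with start ≤ L < stop, and all are concomitant under Section 14.
- The other 9,044 − 262 = 8,782 agree with Section 14.
- If *on* is read as *and*, disagreements rise to 262 + 131 (ongoing drugs started by the last dose) + 3 (drugs started and stopped after it) = 396.
- With branch 3 testing the stop date, or ongoing: 0 without a category and 0 different from Section 14.

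The grid counts show which pattern fails. They do not estimate how many records in the study are affected.

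**The case against.** The best answer is that the SAP states the right rule elsewhere. Section 14 defines post-treatment by the stop date and makes every drug in the gap concomitant. The misprint is visible, because two sub-rules contradict the condition above them. A programmer working from Section 14 would lose nothing. This stands, and it is why the loss is conditional. It does not remove the problem: Appendix 2 holds the explicit assignment algorithm, and nothing says which text prevails.

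A second answer is scope. Appendix 2 is headed as partial-date conventions and Section 14 cites it for that purpose, so complete-date records may never pass through it. That is a fair reading, although the assignment step is not itself limited to partial dates. Even on that reading the imputed stop dates remain in the gap.

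Third, *on* may be a slip in reading the PDF. The point does not depend on it, since the gap is there under the favourable reading. *Start* for *stop* is a different, correctly spelled word.

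A reader might infer three stronger things that the documents do not support:

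- That drugs in use at the end of treatment are lost in general. Those marked ongoing are classified correctly under the *or* reading.
- That prohibited medication would go unnoticed. SAP Section 11 identifies it separately, from data listings and the protocol deviations log.
- That safety results would be distorted. The SAP specifies no movement, mood or QTc analysis that conditions on concomitant-medication status, the table is descriptive, and the primary endpoints in SAP Section 3.2.1 do not use it.

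**Conclusion.** The third branch is wrong as written and conflicts with SAP Section 14. This is an operative classification rule, so it deserves correction even though the intent can be guessed.

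The affected set is non-ongoing medications with a start on or before the last open-label dose and an actual or imputed stop date after it. Under literal use of Appendix 2 all of these are uncategorised and none reaches the concomitant-medication table. The post-treatment flag is lost as well, and the prior flag for drugs started before the first dose.

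The conclusion assumes that the programmer follows Appendix 2 rather than Section 14 and reads *on* as *or*. For drugs with an unknown stop date it also assumes a last contact after the last dose; the documents do not say how often that holds. The number of records affected is unknown. No primary endpoint, sample size or inferential result depends on this rule.

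**What to change.** In SAP Appendix 2, third assignment branch, change *start* to *stop* and *on* to *or*, so that the condition is: medication stop date after the end date of SEP380-303 open-label medication, or ongoing. Keep the three sub-rules unchanged. Appendix 2 then matches Section 14, so no separate statement of precedence is needed.

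The cost is two words. No data collection, table layout or study conduct changes. If classification code has already been written from Appendix 2, one condition in it needs checking.
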